9.7.2.3 Secondary outcomes

- Management and treatment during follow-up period

Frequency of patients with management and treatment during follow-up period will be analyzed.

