Population:	
Patients who meet all of the inclusion criteria and do not meet any of the exclusion criteria will be included in the study population.
 
Inclusion Criteria:
 
 1) Patients diagnosed with at least two fibrosing ILD codes on different dates in the patient identification period from 01-Jan-2013 to 6 months before 28-May-2020 2) Patients aged 18 years and older on the index date 3) Patients for whom data for the 12 months prior to the index date can be extracted as baseline data 
Exclusion Criteria:
 
 1) Patients grouped into the underlying disease of IPF 2) Patients who have met PF-ILD progression criteria during the baseline period 
Note: only diagnosis records without 'suspect flag' are to be considered for evaluating diagnosis related in/excl criteria"

Variables:	
The following information will be extracted from MDV database in this study; sex, age, comorbidity and medical history of interest, Underlying disease (pre-specified ILD), clinical examination, treatment and management of interest

Data sources:	
The MDV database consists of anonymized administrative claims and Diagnosis Procedure Combination (DPC) data for inpatient and outpatient settings from acute hospitals (mainly considered as advanced treatment hospitals). The database includes >35 million patients from >400 hospitals. Patients in Japan have free access to health care facilities and data from the other hospitals not included in the database are unavailable.

Study size:	
The planned sample size is not based on the formal statistical hypothesis testing and statistical precision. Because the MDV database consists of >35 million patients, it is expected that the sufficient number of non-IPF fibrosing ILD patients will be included in the study.

Data analysis:	
Primary outcome Incidence probability of progression to PF-ILDs at 6, 12, 18, and 24 months after the index date. Cumulative incidence probability will be estimated by using Kaplan-Meier method.
 
Secondary outcomes Management and treatment during follow-up period Frequency of patients with management and treatment of interest during follow-up period will be analyzed descriptively.

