9. RESEARCH METHODS

9.1 STUDY DESIGN

This is a retrospective cohort study using the database from MDV.

Data from 01-Jan-2012 to 28-May-2020 will be used. It will be considered that each patient is observable from his/her first encounter to his/her last encounter in the database. The patients with fibrosing ILD will be identified in the period from 01-Jan-2013 to 6 months before 28-May-2020. Each patient who meets all the inclusion criteria and none of the exclusion criteria will be followed up from the day after the index date* until the end of study period (i.e. 28-May-2020), the last encounter in the MDV database, in-hospital death, whichever occurs first.

*The index date will be the date of the second diagnosis of fibrosing ILD. Please refer to the Section 9.2.2.1 for the detailed codes of fibrosing ILD.

*The index date will depend on the time the patient fulfils the eligibility criteria

Figure 1 . Schematic of the Study Design

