9.7 DATA ANALYSIS

9.7.1 Common handling for statistical analysis

Unless otherwise specified, descriptive analysis is planned.

The summary statistics for continuous variables are N, mean, standard deviation, minimum, 25th percentile (Q1), median, 75th percentile (Q3), and maximum.

Tabulations of frequencies for categorical variables will include all possible categories and will display the number of observations in a category as well as percentage (%) relative to the population analysed. The precision for percentage will be one decimal point.

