9.7.2.2 Primary outcome

- Incidence probability of progression to PF-ILDs at 6, 12, 18, and 24 months after the index date

Cumulative incidence probability of progression to PF-ILD at 6, 12, 18 and 24 months after the index date will be estimated by using Kaplan-Meier method. Greenwood's variance estimate will be used for calculating 95% confidence interval. Kaplan-Meier curve will also be displayed.

Of the patients with progression to PF-ILD, frequency of patients meeting each criteria of progression to PF-ILD will be analysed descriptively.

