9.7.3 Subgroup analysis

The three subgroup analyses by underlying diseases defined by disease codes on the index date and 12-months lookback period as described in Annex 5 will be performed for patient background characteristics and treatment, primary outcome, and secondary outcomes.

<Subgroup Patterns>

Underlying Autoimmune Disease (Subgroup1): Autoimmune ILD, Non-autoimmune ILD, Multiple, Unknown

ILD Category (Subgroup 2): Hypersensitive pneumonitis, Exposure-related ILD, iNSIP, Unclassifiable IIP, Sarcoidosis, RA-ILD, SSc-ILD, MCTD-ILD, Other autoimmune ILD, Other ILD, Multiple, Unknown

Pre-Specified ILD Clinical Diagnosis (Subgroup 3): Hypersensitive pneumonitis, Exposure-related ILD, iNSIP, Unclassifiable IIP, Sarcoidosis, RA-ILD, SSc-ILD, MCTD-ILD, SLE-ILD, PM/DM-ILD, Sjogren ILD, Other autoimmune ILD, Other ILD, Multiple, Unknown

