9.9 LIMITATIONS OF THE RESEARCH METHODS

The MDV database does not have pulmonary function test results and there have been no evidence on the validated algorithm to define fibrosing ILD patients other than IPF and progression to PF-ILD as events by using claims data. Therefore, the estimated incidence in this study might be biased and the sensitivity analysis by using different algorithm is planned to assess the robustness of the results.

Due to the characteristics of health care system in Japan as described in Section 9.4, data generated in the clinics/hospitals other than hospitals included in the MDV database are not captured and the incidence probability and frequency might be underestimated.

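### The secondary outcome is a crude ever-recorded percentage over follow-up of unequal length, so it has no common time horizon and can partly reflect how long patients were observed

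*Combined protocol and SAP*

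**What the plan says.** The analysis of the secondary outcome is one sentence in section 9.7.2.3: "Frequency of patients with management and treatment during follow-up period will be analyzed". The abstract (section 4) says the same and adds only that it is descriptive: "Frequency of patients with management and treatment of interest during follow-up period will be analyzed descriptively". Under section 9.7.1, frequency tables will "display the number of observations in a category as well as percentage (%) relative to the population analysed", so every patient counts fully in the denominator, however briefly observed.

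Section 9.1 sets the observation period. On entry: "The patients with fibrosing ILD will be identified in the period from 01-Jan-2013 to 6 months before 28-May-2020". Follow-up starts the day after index and runs "until the end of study period (i.e. 28-May-2020), the last encounter in the MDV database, in-hospital death, whichever occurs first". No minimum follow-up is required.

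The primary outcome is treated differently. In section 9.7.2.2 the cumulative incidence of progression at 6, 12, 18 and 24 months "will be estimated by using Kaplan-Meier method".

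Section 9.7.3 says that the three subgroup analyses "will be performed for patient background characteristics and treatment, primary outcome, and secondary outcomes". Section 9.7.4 repeats all analyses with a later data cut-off, with the index moved to the first diagnosis code, and with both changes. Section 9.7.2.1 summarises duration of follow-up among the background characteristics, so section 9.7.3 extends that summary to the subgroups.

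**The concern.** The share of patients with at least one claim rises with the time available to record one. When patients are observed for different lengths of time, a crude percentage answers no fixed question such as how many start home oxygen within a year. Two groups that start an item at the same rate will show different percentages if one is observed for longer.

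This bears on three results: the overall percentage for each item, the comparison a reader will naturally make across 4, 12 and 15 subgroup categories, and the comparison of the main analysis with its sensitivity analyses. A later cut-off lengthens follow-up for patients who were still being seen at 28-May-2020, and may also admit recent patients with short follow-up. An earlier index date lengthens follow-up directly. In each case a percentage can move without any change in practice.

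Loss from view is a real possibility here, because section 9.9 notes that "data generated in the clinics/hospitals other than hospitals included in the MDV database are not captured". A patient who transfers elsewhere ends follow-up at the last recorded encounter.

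**Working it through.** The documents give no figure for this outcome to reproduce. The check has a date calculation from the plan's own rules and an illustration with assumed rates.

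**Potential follow-up (section 9.1)**

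- The latest index date is 6 months before 28-May-2020, that is 28-Nov-2019. To 28-May-2020 this is 182 days, or 0.50 years.
- The earliest index date is 02-Jan-2013, because two codes on different dates are needed from 01-Jan-2013. To 28-May-2020 this is 2,703 days, or 7.40 years.
- The ratio is 2,703 / 182 = 14.9.
- The index window is 2,703 − 182 = 2,521 days. Its last 549 days (from 28-May-2018) allow less than 24 months: 549 / 2,521 = 22%. Its last 184 days (from 28-May-2019) allow less than 12 months: 184 / 2,521 = 7%.

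These are upper limits on each patient's follow-up. Last encounter or in-hospital death shortens them.

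**Crude percentage when all patients have the same follow-up T and a constant rate r (assumed)**

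Expected share = 1 − exp(−rT).

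| r per year | T = 2 years | T = 3 years |
|---|---|---|
| 0.05 | 9.5% | 13.9% |
| 0.10 | 18.1% | 25.9% |
| 0.20 | 33.0% | 45.1% |

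For a rare item at an assumed 0.005 per year, the shares are 1 − exp(−0.01) = 1.0% and 1 − exp(−0.015) = 1.5%.

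**Crude percentage with staggered entry and loss (assumed)**

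Let index dates be uniform over the window, so that T is uniform from 0.5 to 7.4 years, and let patients be lost at rate m. The expected share is the mean over T of [r/(r+m)] × [1 − exp(−(r+m)T)]. At r = 0.10 per year:

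- m = 0: 31.3%
- m = 0.3: 18.0%
- m = 1.0: 8.4%

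The corresponding spans are 17.5% down to 4.4% at r = 0.05, and 50.9% down to 15.6% at r = 0.20. If the losses are uninformative censoring, the 24-month cumulative incidence at r = 0.10 is 1 − exp(−0.2) = 18.1% in all three cases.

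**Does a fixed horizon deal with early death?**

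Not by itself. With death as a competing event at rate d, 24-month cumulative incidence is [r/(r+d)] × [1 − exp(−2(r+d))]. At r = 0.2 it is 33.0% for d = 0, and (0.2/0.5) × (1 − exp(−1)) = 25.3% for d = 0.3. First occurrences divided by patient-years at risk give 20 per 100 patient-years in both cases. The two measures are therefore needed together.

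**The case against.** The outcome is descriptive, and no test, contrast or ranking between subgroups is planned. All subgroups share one identification window and one cut-off, and follow-up duration will be tabulated by subgroup. The period is also defined for each patient. Several items are components of the primary event, which already has fixed-time estimates by subgroup.

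Much of this stands. A reader might infer that the subgroup percentages cannot be compared at all. The documents do not support that, because it requires a material imbalance in follow-up between subgroups and no follow-up distribution is given. A reader might also set the design extremes against each other: at 0.2 per year, 0.5 year gives 9.5% and 7.4 years gives 77.2%. That contrasts two individual patients at an assumed rate. A reported percentage averages over a group's mix of follow-up, so differences between groups would normally be far smaller. For a rare item the whole span is small: at 0.005 per year it is 0.2% to 3.6%.

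What does not stand is the view that being descriptive removes the problem. A period defined patient by patient is not a common horizon, and the overall percentage lacks one even if the subgroups are balanced. The duration table discloses an imbalance without correcting it. The Kaplan-Meier estimate for the composite says nothing about individual items.

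**Conclusion.** The point holds in a limited form. The planned percentages have no common time horizon. Differences between subgroups, or between the main and sensitivity analyses, may partly reflect follow-up length and should not be read without it.

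The range of potential follow-up, about 0.5 to 7.4 years, follows from the plan's dates. The effect on any reported percentage does not, because it depends on item rates and subgroup follow-up that the documents do not give. The contrast of 33% with 45% is an illustration that assumes 0.2 per year, a constant rate, and 2 or 3 years of follow-up for everyone. Across assumed rates of 0.05 to 0.20 per year the same contrast is 4 to 12 percentage points.

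This weakens interpretation of the secondary objective. It does not affect the primary estimate. It should be changed because the remedy is cheap.

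**What to change.** In section 9.7.2.3, with a matching line in the abstract, define the analysis of each management and treatment item as follows, overall and by subgroup:

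- Cumulative incidence of the first occurrence at 6, 12, 18 and 24 months after index, with in-hospital death as a competing event and censoring at last encounter or end of study.
- The number of first occurrences per 100 patient-years at risk. This removes the dependence on early death and short observation as long as the rate is roughly constant over follow-up.
- The crude count and percentage as a supplementary column, shown with follow-up duration.

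First occurrence needs a definition where Table 2 sets no new-claim condition. Nintedanib is the clearest case. Table 1 does not count its claims up to 28-May-2020 as progression, so the second exclusion criterion does not remove earlier users. For such items, either show users in the baseline window separately or label the estimate as first recorded claim after index.

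The claim dates, follow-up rules and reporting times are already needed for the primary outcome, so no new data are required. The cost is plan wording, modest programming for the competing-event estimates and rates, and more tables. Estimates will be sparse for rare items and small subgroups.

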9.7.3 Subgroup analysis

The three subgroup analyses by underlying diseases defined by disease codes on the index date and 12-months lookback period as described in Annex 5 will be performed for patient background characteristics and treatment, primary outcome, and secondary outcomes.

<Subgroup Patterns>

Underlying Autoimmune Disease (Subgroup1): Autoimmune ILD, Non-autoimmune ILD, Multiple, Unknown

ILD Category (Subgroup 2): Hypersensitive pneumonitis, Exposure-related ILD, iNSIP, Unclassifiable IIP, Sarcoidosis, RA-ILD, SSc-ILD, MCTD-ILD, Other autoimmune ILD, Other ILD, Multiple, Unknown

Pre-Specified ILD Clinical Diagnosis (Subgroup 3): Hypersensitive pneumonitis, Exposure-related ILD, iNSIP, Unclassifiable IIP, Sarcoidosis, RA-ILD, SSc-ILD, MCTD-ILD, SLE-ILD, PM/DM-ILD, Sjogren ILD, Other autoimmune ILD, Other ILD, Multiple, Unknown

9.7.4 Sensitivity analysis

- 1) The end of data extraction period will be changed from 28-May-2020 to the latest data cut off. OFEV was approved for PF-ILD on 29-May-2020, and the characteristics of claims data before and after the above approval for new indications might not be different. To increase the sample size, all the analyses will be repeated with this data extraction period.
- 2) The index date will be changed from the date of the second code of fibrosing ILD to the date of the first code of fibrosing ILD because there might be patients who are asked to visit hospitals annually after the first diagnosis. All the analyses will be repeated with this index date.

In addition, all the analyses will be repeated with both data extraction period and index date changed.

After exploring the proxy patterns among patients meeting the criteria of progression to PF-ILD as described in Section 9.7.2.2, a sensitivity analysis with modified progression criteria might be performed.

9.8 QUALITY CONTROL

The analysis program and the data codes used in the analysis will be checked by someone different from the creator.

9.9 LIMITATIONS OF THE RESEARCH METHODS

The MDV database does not have pulmonary function test results and there have been no evidence on the validated algorithm to define fibrosing ILD patients other than IPF and progression to PF-ILD as events by using claims data. Therefore, the estimated incidence in this study might be biased and the sensitivity analysis by using different algorithm is planned to assess the robustness of the results.

Due to the characteristics of health care system in Japan as described in Section 9.4, data generated in the clinics/hospitals other than hospitals included in the MDV database are not captured and the incidence probability and frequency might be underestimated.

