9.2.2 Study population

9.2.2.1 Eligibility criteria

Patients who meet all of the inclusion criteria and do not meet any of the exclusion criteria will be included in the study population.

Inclusion Criteria:

- 1) Patients diagnosed with at least two fibrosing ILD codes^{*1} on different dates in the patient identification period from 01-Jan-2013 to 6 months before 28-May-2020
- 2) Patients aged 18 years and older on the index date
- 3) Patients for whom data for the 12 months prior to the index date can be extracted as baseline data

*1 International Statistical Classification of Diseases and Related Health Problems (ICD-10) code or disease code: J84.1, J84.9, 8844510, 8848382, 8844341, 8848278, 8836513, 8848267, 8848302, 8839362, 8848283, 8837013, 8834158, 8848245, 8840951, 8847737

Exclusion Criteria:

- 1) Patients grouped into the underlying disease of IPF^{*1}
- 2) Patients who have met PF-ILD progression criteria during the baseline period

*1 Please refer to the ANNEX 5 for algorithm to define underlying diseases

Note: only diagnosis records without 'suspect flag' are to be considered for evaluating diagnosis related in/excl criteria"

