9.3 VARIABLES

9.3.1 Outcomes

9.3.1.1 Primary outcome

Incidence probability of progression to PF-ILDs at 6, 12, 18, and 24 months after the index date*

Progression to PF-ILD as event in this study is defined in Table 1 as well as Annex 2. Event date will be the date when the one of criteria of the progression to PF-ILD is met.

*The index date will be the date of the second diagnosis of fibrosing ILD. Please refer to the Section 9.2.2.1 for the detailed codes of fibrosing ILD.

Table 1. Interstitial lung disease progression proxies

Proxy
- ≥ 3 pulmonary function tests on different dates of service within 365 days - The date of the 3 rd pulmonary function test will be the date of progression
- ≥ 3 HRCT/CT on different dates of service within 365 days - The date of the 3 rd HRCT/CT will be the date of progression
≥ 1 claim for oxygen therapy (HOT) during follow-up period
≥ 1 respiratory hospitalization during follow-up period
≥ 1 claim for palliative care during follow-up period
≥ 1 lung transplant during follow-up period
≥ 1 new* claim for immunosuppressive drugs during follow-up period with at least two out of the three test codes** within 3 months before new claims for immunosuppressive drugs Rituximab Tacrolimus Mycophenolate Cyclosporine Cyclophosphamide Azathioprine Tocilizumab
*: Not received in the 12 months prior to the index date **: ① Pulmonary function tests, ② HRCT/CT, ③ KL-6 or SP-D
≥ 1 new* claim for oral corticosteroid with a prednisone-equivalent dose of >20 mg during follow-up period and with at least two out of the three test codes* within 3 months before new claims for oral corticosteroid *: Not received in the 12 months prior to the index date **: ① Pulmonary function tests, ② HRCT/CT, ③ KL-6 or SP-D
≥ 1 claim for Nintedanib* during follow-up period *: Patients meeting this criterion will be counted only if patients with fibrosing ILDs meet this criterion on or after 29-May-2020, because nintedanib was approved for PF-ILD on 29-May-2020. Even if patients with fibrosing ILDs meet this criterion on or before 28-May-2020, they will not be counted.

HRCT; high-resolution computed tomography, CT; computed tomography, KL-6; krebs von den lungen-6, SP-D; surfactant protein D

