9.4 DATA SOURCES

The MDV database consists of anonymized administrative claims and DPC data for inpatient and outpatient settings from acute hospitals (mainly considered as advanced treatment hospitals). At present, the database includes >35 million patients from >400 hospitals. Patients in Japan have free access to health care facilities and data from the other hospitals not included in the database are unavailable.

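### Care received outside MDV before index can raise the cumulative incidence of progression, so section 9.9 should not name underestimation as the only direction of bias

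*Combined protocol and SAP*

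**What the plan says.** Five rules in the protocol bear on this point.

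- **Observability (section 9.1).** "It will be considered that each patient is observable from his/her first encounter to his/her last encounter in the database". Nothing is required inside that span.
- **Index date (section 9.1).** "The index date will be the date of the second diagnosis of fibrosing ILD".
- **Baseline (section 9.2.2.1).** Inclusion 3 admits "Patients for whom data for the 12 months prior to the index date can be extracted as baseline data", with no minimum number of contacts in the window. Exclusion 2 removes "Patients who have met PF-ILD progression criteria during the baseline period".
- **Event definition (section 9.3.1.1, Table 1).** Immunosuppressants and oral corticosteroids count only if new, defined as "Not received in the 12 months prior to the index date", and only with two of three test types recorded in the preceding 3 months. Home oxygen needs just "≥ 1 claim for oxygen therapy (HOT) during follow-up period", with no new-user condition.
- **Data capture (section 9.4).** "data from the other hospitals not included in the database are unavailable".

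On the consequence of that last rule, section 9.9 says that outside records "are not captured and the incidence probability and frequency might be underestimated". The paragraph before it says the incidence may be biased, without a direction, but for a different reason: the claims algorithms for the cohort and the event are not validated.

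**The concern.** Absence of a claim is doing two jobs. After index, a missing claim hides an event, which is the case section 9.9 describes. Before index, a missing claim makes a patient look free of progression and untreated, so exclusion 2 and the washout are passed by default. If that patient later has the same care at an MDV hospital, the earliest record of it there is dated as progression.

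The affected quantity is the primary outcome. Someone who relies on the care-elsewhere paragraph alone would take the reported incidence to be, if anything, too low. If the pre-index path is material, that reading is unsafe, most of all at 6 and 12 months, where such events would tend to fall.

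**Working it through.** **1. Is the path open under the eligibility rules?**

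- A patient whose first MDV encounter is the transfer, and whose second fibrosing-ILD code follows within 12 months, fails inclusion 3 and is not in the cohort.
- A patient with one earlier MDV contact for any reason, say 14 months before index, is observable for the whole baseline year under section 9.1, even with no record in it. Shared care or sparse visits have the same effect. Section 9.7.4 itself accepts that some patients may be seen only yearly after the first diagnosis.
- Because index is the second code, an MDV oxygen or drug claim made between the two codes, and within 12 months before index, falls in baseline. It then triggers exclusion 2 or makes the drug not new. The path therefore also needs the first MDV oxygen or drug claim to come after the second code.

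The path is narrowed but not closed. It is widest for home oxygen, which has no new-user or test condition.

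**2. Does a planned analysis test it?** The two defined runs in section 9.7.4 change the data cut-off and the index code. Moving to the first code shifts the baseline window earlier and moves claims between the codes into follow-up, so it alters the path without isolating it. The possible run with modified progression criteria is unspecified and concerns the proxies, not baseline capture.

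**3. Direction and size.** The plan gives no expected incidence, sample size or precision target (section 9.5), so there is no figure to reproduce. All inputs below are assumptions, taken at one fixed time point and with independent censoring:

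- I: true risk in patients who had not progressed
- m: share of the analysed cohort already progressed or treated elsewhere
- q: probability that such a patient meets a proxy in MDV by that time
- s: share of true follow-up events captured

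Observed risk = (1 − m)·s·I + m·q.

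With full capture (s = 1) the bias is m·(q − I): upward if q > I, downward if q < I.

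| I | q | m = 2% | m = 5% | m = 10% |
|---|---|---|---|---|
| 20% | 90% | 21.4% | 23.5% | 27.0% |
| 40% | 90% | 41.0% | 42.5% | 45.0% |
| 40% | 10% | 39.4% | 38.5% | 37.0% |

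For example, 0.95 × 0.20 + 0.05 × 0.90 = 0.235.

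**4. Net of missed events.** Setting observed risk equal to I gives the share at which the two biases cancel: m = I(1 − s)/(q − sI).

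| I | q | s = 95% | s = 90% | s = 80% |
|---|---|---|---|---|
| 20% | 90% | 1.4% | 2.8% | 5.4% |
| 20% | 70% | 2.0% | 3.8% | 7.4% |
| 40% | 90% | 3.8% | 7.4% | 13.8% |

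For example, 0.20 × 0.05/(0.90 − 0.95 × 0.20) = 0.010/0.71 = 1.4%. Above the tabulated share the estimate is too high; below it, too low.

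**5. Timing.** If q is reached early while I is still growing, the excess is larger at the early time points. With m = 5% and q = 90% by 6 months, a risk of 20% at 6 months gives 0.05 × 0.70 = 3.5 points. A risk of 40% at 24 months gives 0.05 × 0.50 = 2.5 points.

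**The case against.** The other side has real force on five matters.

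- **Eligibility.** A reader might infer that anyone moving to an MDV hospital with established oxygen or drug treatment is counted as a new case. The documents do not support that: inclusion 3 and the second-code index remove many such patients. This stands and limits the point to the groups named above.
- **Drug proxies.** Two test types must be recorded within 3 months before the claim. If they come from an admission whose qualifying diagnosis is J84.x, that admission is itself a proxy in Annex 2: it excludes the patient before index, and is already an event after it. This stands; the drug path is the weaker one.
- **Direction.** A reader might infer that the path always overestimates. It does so only when q exceeds I. Patients whose care stays elsewhere dilute the estimate, as the 40% to 37% example shows.
- **Section 9.9.** It is hedged, never claims a lower bound, and contains a non-directional bias statement. That is so, but the non-directional statement concerns algorithm validity. On care elsewhere, one direction is all that is offered.
- **Existing and proposed output.** Section 9.7.2.2 already gives the Kaplan-Meier curve and proxy frequencies, but neither links timing to proxy. The proposed filter cannot prove that care was not supplied elsewhere. It also removes yearly attenders and favours frequent ones, so a changed estimate could not be attributed to prevalent cases alone. That is a reason to treat the run as supportive, not to omit it.

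**Conclusion.** The point holds in limited form. Baseline status and washout rest on recorded MDV claims with no minimum contact, so some patients can enter with unseen progression or treatment and have continuing care counted as incident progression. This can overestimate early cumulative incidence when such patients meet a proxy more often than the true risk. Missed care after index works the other way. The documents give none of m, q, s or I, so the size and the net direction are unknown, and naming only underestimation is not supported.

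The illustrations show only that small shares could matter: 1.4% to 5.4% cancels the loss at 20% true risk with q at 90% and capture of 95% to 80%. They are not evidence that such shares exist. A reader might go further and conclude that the reported incidence will be too high overall; the documents do not support that either. The point calls for a cheap improvement to the limitations and the sensitivity set, not a change to the primary analysis.

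**What to change.** 1. **Section 9.9.** Replace the one-directional statement with this: care outside MDV after index can hide events and bias incidence downward; care outside MDV before index can let already progressed or treated patients enter and bias it upward; the net direction is unknown.
2. **Section 9.7.4.** Add a firm sensitivity run limited to patients with at least one MDV encounter in each half of the 12 months before index (days −365 to −183 and −182 to −1). Report the number removed, the 6-, 12-, 18- and 24-month estimates, and the timing of first events by proxy. A cluster soon after index would suggest, though not prove, prevalent cases.
3. **Caveat to state with the run.** It controls the bias only in part, and it favours frequent attenders, who have more chances to meet the test-count proxies. It supports the primary analysis and does not replace it.

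The cost is a short text change, one filter on data already held and one added tabulation. The downside is a smaller, more selected cohort in that run.
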